6. TREATMENT DESCRIPTION

The standardized multidisciplinary method under study is a weight loss program consisting of different stages. The initial stage (stage 1) is based on a protein diet, a type of ketogenic diet very low in calories. This stage is followed by a physiological adaptation stage (stage 2) in which all food groups are reintroduced progressively, and a maintenance phase (stage 3) with long-term monitoring of the patient's weight to ensure stability of the results obtained. This program contemplates other essential aspects in the management of obese patients, such as dietary education, physical activity and psychological support throughout the treatment.

80% of target weight loss			20% of target weight loss	Long-term maintenance of weight loss
Multidisciplinary team (dietary counselling / physical activity / psychological support)				
Stage 1 Active Stage		Stage 2 Dietary re-education		Stage 3 Maintenance
Phase 1	Phase 2	Phase 3	Gradual re-introduction of different foods	
VLCK diet ¹ (600-800 kcal/day)		LC diet ² (800-1500 kcal/day)		Maintenance diet (1500-2250 kcal/day)

The stage 1 protein diet is established through the intake of high biological value proteins and low-glycaemic vegetables, supplemented with micronutrients (potassium, sodium, calcium, magnesium, vitamins and trace elements) to avoid deficiencies. This stage consists of 3 phases (Phase 1, Phase 2a and Phase 2b), in which a protein preparation and then a second protein preparation are replaced progressively by protein-rich natural foods (meat/fish/eggs). During this period of ketogenic diet, the patient will be visited by the doctor every fortnight.

The ketogenic stage 1 of the method will be maintained for 2 months for those patients with an initial BMI of 30 to 35 kg/m² and for 3 months for those patients with initial BMI > 35 kg/m².

Stage 2 begins after the initial loss of most of the weight to be lost (ideally 80%), with the progressive introduction of different foods, while reducing protein preparations at the same time. In this way the weight loss indicated by the doctor is finally reached and the food balance is also achieved. This stage will be maintained for a period of 4 months in patients with an initial BMI of 30 to 35 kg/m² and for 6 months for those patients with initial BMI > 35 kg/m².

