7.2. Follow-up period

The expected follow-up period for each patient will be 2 years from the time of inclusion, recording data during the weight loss and maintenance periods. The registry of patient data for this study will be made by the doctor and the dietitians/nutritionists who will regularly see the patient in the face-to-face visits at the Pronokal centre. For this, a specific form will be designed in which information about the variables to be studied will be collected.

Before starting treatment with the standardized multidisciplinary method and its inclusion in the study, the physician will have performed a first patient pre-inclusion visit (day -15) to request complementary tests (laboratory and ECG) and rule out the existence of contraindications to the ketogenic diet part of the weight loss program.

The study will begin with the baseline visit (day 0) in which the inclusion and exclusion criteria will be confirmed, the signing of informed consent will be obtained and the multidisciplinary treatment will be prescribed, followed by 6 control visits: 2 visits during the ketogenic stage (1-month after the start and at the end of ketosis), 2 visits during the physiological adaptation phase (at 4 or 5 months and at the end of stage 2) and 2 follow-up visits during the maintenance up to the 2-year completion. Regardless of the visits established in this protocol, the doctor will make as many visits as he/she deems necessary for good patient control.

On the other hand, dietitians/nutritionists, according to the methodology of the program, will carry out a face-to-face follow-up of the patient, which will be fortnightly during the ketogenic diet, monthly during the physiological adaptation of stage 2 and quarterly or semi-annual during the maintenance stage.

In the **pre-inclusion visit (day -15)**, the physician will perform a first clinical assessment of the patient. He/she will record the sociodemographic data, history of diabetes, comorbidities, pharmacological treatments. He/she will request complete laboratory tests and will perform an electrocardiogram to rule out contraindications and verify the inclusion/exclusion criteria. The said laboratory tests will include:

- Complete blood count and leukocyte formula
- Hydrocarbon metabolism: fasting glycemia, HbA1c, insulinemia
- Lipid profile: total cholesterol, LDL-C, HDL-C, triglycerides
- Transaminases: GOT, GPT, gammaGT

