- Renal profile: creatinine, glomerular filtration, creatinine clearance, microalbuminuria
- Nitrogen balance: urea, uric acid
- Thyroid profile: TSH, T3, T4
- Ionogram: Na, K, Cl, Ca, Mg

In the **initial visit (day 0)**: In this visit, a physical examination will be performed and data related to weight (weight, BMI, waist circumference), as well as data on comorbidities associated with obesity (type of pathology, pharmacological treatment, complications in the last year) will be recorded. After checking the inclusion/exclusion criteria, the patient information sheet will be given and the informed consent will be obtained. During this visit, the patient's quality of life will be assessed (with the SF-12 quality of life questionnaire) and treatment will be prescribed according to the method (PronoKal® Method), which will begin with phase 1 of the active stage.

PRONOCOST study. Cost-effectiveness pharmacoeconomic study of a standardized multidisciplinary weight loss method (PronoKal® Method) to improve health condition of obese patients with associated comorbidities.

In the **follow-up visits - Recorded by the doctor**. In the regular check-ups throughout the course of treatment, the physician will record: any discomfort or side effect related to weight loss treatment and whether there has been any change in the comorbidities associated with obesity (laboratory results, medication, complications, etc.). At the end of each stage the doctor will assess the patient's quality of life through a questionnaire.

In the **follow-up visits - Recorded by dietitians/nutritionists**. During the interviews that the dietitians/nutritionists will have with the patients, and parallel to the doctor's records, the following details will be recorded:

- Clinical data: anthropometric data and blood pressure
- Medication changes
- Onset of complications (e.g., hypertensive crisis, ...)
- Hospital admissions
- Work absenteeism: number of days and cause....

In case of early withdrawal from the study, the doctor will write the dropout date and the reason, in study completion form.

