10.2. Analysis of objectives

The primary objective analysis will include:

- Costs of weight loss treatment estimated from the cost of: protein products and dietary supplements + number of control visits + number of laboratory tests performed
- Healthcare expenditure estimated as the sum of the following costs: pharmacological treatment of associated comorbidities, incidence of

complications (visits to his/her primary care physician, a specialist or emergency department for acute complications, treatment of acute complications, number of hospital admission days, antibiotic treatment), consumption of health resources (visits to the general practitioner, visits to specialists, laboratory tests)

- Work absenteeism, estimate of the number of work leave days + hours of work absenteeism due to health problems or medical visits.

In order to evaluate if the weight loss treatment is improving the health of patients and reducing health expenditure and absenteeism, the healthcare expenses and work absenteeism estimated from the doctor's records corresponding to the 6 months prior to the initiation of the weight loss treatment will be compared with data recorded at follow-up visits over the 2-year follow-up. Likewise, the doses and number of drugs required by patients for the treatment of their comorbidities before the weight loss and at the control visits during weight loss and up to completing the 2 years of follow-up will be compared.

As secondary objectives, the efficacy of the weight loss treatment will be studied by comparing the anthropometric parameters of the initial visit with those of the follow-up visits (weight, body mass index and waist circumference). Likewise, any improvement in laboratory parameters and blood pressure during the follow-up will be studied. Changes in quality of life scores (SF-12) will also be assessed between the initial visit and the end of each treatment stage.

For all objectives, the comparisons between qualitative variables will be made using the Chi square test or the Fisher exact test, and the comparison between quantitative variables will be performed using the Student's t-test (in the case of 2 groups) or by the one-way ANOVA test (for 3 or more groups). If the conditions for the Student's t-test or the Anova test are not met, the non-parametric Mann-Whitney U test (2 groups) or the Kruskal-Wallis test (for 3 or more groups) will be used.

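### The primary before-after comparison of expenditure and absenteeism sets 6 months against 2 years with no common time unit, no withdrawal rule and no paired test

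*Combined protocol and SAP*

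**What the plan says.** Section 10.2 (Analysis of objectives) defines the expenditure outcome by addition: "Healthcare expenditure estimated as the sum of the following costs: pharmacological treatment of associated comorbidities", followed by the costs of complications and of health resource use. Absenteeism is likewise a count, leave days plus hours missed. The effect on both is judged by taking the values "corresponding to the 6 months prior to the initiation of the weight loss treatment will be compared with data recorded at follow-up visits" across the 2 years.

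For quantitative variables 10.2 names Student's t-test for 2 groups or one-way ANOVA for 3 or more. If their conditions fail, "the non-parametric Mann-Whitney U test (2 groups) or the Kruskal-Wallis test (for 3 or more groups) will be used". No paired method is named.

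Section 7.2 (Follow-up period) sets six control visits by the doctor. Four fall before the end of stage 2, and then there are "2 follow-up visits during the maintenance up to the 2-year completion". Dietitian contacts are "fortnightly during the ketogenic diet, monthly during the physiological adaptation of stage 2 and quarterly or semi-annual during the maintenance stage". Absenteeism and hospital admissions are listed among the dietitians' records.

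On withdrawal, 7.2 covers data collection only: "In case of early withdrawal from the study, the doctor will write the dropout date and the reason, in study completion form". Sections 10.1 and 10.2 give no analysis set and no rule for incomplete follow-up.

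**The concern.** A sum of costs or a count of days grows with the time over which it is collected. Comparing one taken over 6 months with one taken over up to 24 months needs a stated unit, and there is none. The size of the apparent effect, and even its direction, then depends on which reading the analyst chooses.

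Section 9.1 lists three primary endpoints. Two of them, health resource use and absenteeism, rest on this comparison, as does the expenditure side of the cost-effectiveness objective in 3.1. The design has no control group, so the before-after contrast is the plan's only evidence that expenditure or absence fell.

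**Working it through.** The plan states no effect size, SD, dropout rate or expected ratio, so there is no figure of its own to reproduce. All ratios below are follow-up divided by baseline for a patient whose monthly use does not change, unless stated otherwise.

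**Inputs.** Baseline 6 months and follow-up 24 months (10.2). Stage 1 lasts 2 or 3 months and stage 2 lasts 4 or 6 months, for initial BMI 30-35 or above 35 (section 6). Visit schedule from 7.2. Dropout rates are assumed.

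**1. Read as totals.** Ratio = months observed / 6.
- Completer: 24/6 = 4.0. With a true 50% cut: 4.0 × 0.5 = 2.0. The monthly rate must fall by more than 1 − 6/24 = 75% before any saving appears.
- Withdrawal at 12 months: 12/6 = 2.0. At 6 months: 6/6 = 1.0. At 3 months: 3/6 = 0.5.
- If a fraction d withdraws evenly over 24 months (mean 12 months), the mean ratio is 4(1 − d) + 2d. For d = 0, 20, 40 and 60% this gives 4.0, 3.6, 3.2 and 2.8. With a true 50% cut: 2.0, 1.8, 1.6 and 1.4.

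**2. Read visit by visit.** This assumes that each visit captures only the time since the last one, which the plan does not say.
- Stage 2 ends at 2 + 4 = 6 months or 3 + 6 = 9 months. With the first stage 2 visit at month 4 (lower BMI group) or 5 (higher), the doctor's protocol visits fall at months 1, 2, 4, 6 or 1, 3, 5, 9.
- Intervals of 1, 1, 2, 2 or 1, 2, 2, 4 months, divided by 6, give ratios of 0.17 to 0.67 (up to 0.83 if months 4 and 5 are swapped). All are false savings.
- In maintenance, two visits cover 24 − 6 = 18 or 24 − 9 = 15 months, on average 9 or 7.5 months each if the last is at month 24. Ratios: 9/6 = 1.5 and 7.5/6 = 1.25.
- Dietitian contacts (about 0.46, 1, 3 and 6 months) give 0.08, 0.17, 0.50 and 1.0. None exceeds 1.

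**3. Per month of observed time.** Ratio = (total / months observed) / (baseline total / 6) = 1.0 for an unchanged patient, whether observed for 3, 6, 12 or 24 months.

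**4. Choice of test.** Simulation with all inputs assumed: 200 patients; gamma-distributed patient means with CV 1, 1.5 or 2, paired with gamma monthly values with CV 2, 3 or 4; dropout 0 or 40%; 1,000 trials per scenario.
- Totals, no effect: a significant false rise in 95-100% of trials (Student's t) and 100% (Mann-Whitney).
- 24-month rate against 6-month rate by Mann-Whitney, no effect: a false rise in 36/85/99% without dropout and 12/39/71% with 40% dropout. The longer average is less skewed, so the ranks shift although the mean does not.
- The same with 30-50% of spend constant from month to month (assumed): 0-1%.
- Paired analysis of observed-time rates, no effect: significant in roughly 3-7% of trials.

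**The case against.** **Totals are not prescribed.** A reader might infer that the plan will report a fourfold rise. The text does not say so; it leaves the unit open, and a careful analyst might well use a rate. That limits the claim to a missing definition with large consequences. It does not remove the problem, because nothing in the plan requires a rate and no paired test is named.

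**Totals do not always inflate.** Withdrawal before 6 months gives a ratio below 1. This stands, and it is why retention alone would move the result.

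**A false rise in maintenance is not general.** A reader might carry the 1.5 and 1.25 over to every outcome. Absenteeism and admissions are among the dietitians' records, taken quarterly or semi-annually in maintenance, where the ratios are 0.50 and 1.0. The higher figures could arise only for items recorded at the doctor's protocol visits. Section 6 also has the doctor seeing patients every fortnight in the ketogenic stage, and 7.2 allows extra visits, so the protocol intervals are not the only contacts.

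**Rates with a rank test are not unsafe everywhere.** The simulated false rise needs sparse, irregular outcomes. Section 5.1 refers to patients treated with two or more drugs, so a recurring share of expenditure is plausible, and the effect then nearly vanishes. The warning holds for sparse outcomes such as absenteeism.

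**The one-year look-back may be harmless.** At day 0 the comorbidity data include "type of pathology, pharmacological treatment, complications in the last year". Section 10.2 already fixes the expenditure baseline at 6 months, and nothing says that this item feeds it. Only if it does is there a mismatch, of 12/6 = 2.0.

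**Conclusion.** The point holds as an undefined primary comparison: no time unit, no matched window, no withdrawal rule, and independent-group tests for a within-patient contrast. It should be settled before analysis.

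The size under a totals reading is exact arithmetic for constant use: 4.0 for a completer and 0.5 for withdrawal at 3 months. A true 50% cut in a completer appears as 2.0. The cohort figures of 4.0 down to 2.8 rest on assumed dropout of 0 to 60%, spread evenly. The visit-by-visit ratios rest on the assumption that each visit covers only the time since the last. The simulation results rest wholly on assumed distributions and serve only to guide the choice of test.

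The documents do not support the inference that totals are the stated method, that absenteeism or admissions would falsely rise in maintenance, or that the look-back periods are certainly inconsistent. The comparison of doses and number of drugs looks at states at given visits and is not affected.

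**What to change.** In 10.2:

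1. Express expenditure and absenteeism in both periods per patient-month (or per 6 months) of observed time, counting each patient up to the recorded dropout date.
2. Compare follow-up with baseline within patient by a paired analysis of the mean difference (paired t-test or bootstrap confidence interval), in place of the independent-group t-test or Mann-Whitney test. Avoid a rank test on rates for sparse outcomes such as absenteeism.
3. Keep the full 2-year follow-up as the main contrast, as 10.2 intends. Report equal windows (months 0-6, 6-12, 12-18, 18-24) as supporting results, with the number contributing to each. A contrast at 18-24 months in completers only would be a weaker main analysis: it omits spending during stages 1 and 2 and, at 40% dropout, 80 of 200 patients.
4. Add a sensitivity analysis for withdrawals, for example with unobserved time set to the patient's own baseline rate. A rate corrects for length of observation, but not for patients leaving because they do badly.
5. If the one-year complications item in 7.2 feeds the baseline cost, reconcile the two look-back periods.

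The cost is about one paragraph in 10.2, possibly a phrase in 7.2, and a little more analysis work. The dropout date is already collected. The window results need dated events; whether the form in Annex 3 records them cannot be confirmed, because the annex is not shown. Late windows also hold fewer patients: with 40% even dropout, 180, 160, 140 and 120 of 200 complete the four windows, from 200(1 − 0.4w/24) at w = 6, 12, 18 and 24.

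### The six-month pre-treatment expenditure window takes in the programme's own day -15 visit and laboratory panel, and the plan does not say where to book them

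*Combined protocol and SAP*

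**What the plan says.** Section 10.2 builds the primary analysis from three components: the cost of the weight loss treatment, healthcare expenditure and work absenteeism. Expenditure and absenteeism in the period "corresponding to the 6 months prior to the initiation of the weight loss treatment" are compared with those recorded over the 2-year follow-up.

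Section 7.2 places a physician visit at day -15, before the baseline visit at day 0 at which treatment is prescribed. At day -15, "He/she will request complete laboratory tests and will perform an electrocardiogram to rule out contraindications". The stated aim is to "rule out the existence of contraindications to the ketogenic diet part of the weight loss program" and to check eligibility.

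In section 10.2, laboratory tests appear in two lists. Healthcare expenditure includes "consumption of health resources (visits to the general practitioner, visits to specialists, laboratory tests", alongside drugs and complications. Treatment cost covers products, control visits and a count of laboratory tests. Section 7.2 uses the term control visits for six visits, all after day 0. Absenteeism includes "hours of work absenteeism due to health problems or medical visits", with no exception for visits made for the programme.

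**The concern.** The work-up is a cost of entering the programme, not usual care of the patient's comorbidities. It falls inside the window that stands for usual care, and nothing in the plan takes it out. The study has no control group, so that window is the only comparator for the primary objective. Every patient has the work-up, so a larger sample does not dilute its effect.

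If the panel and visit are counted as pre-treatment expenditure, while programme visits and tests after day 0 are counted as treatment cost, expenditure appears to fall for a patient whose ordinary care has not changed. The cost of the method is also understated by the same work-up. Both errors would favour the method in a cost-effectiveness comparison.

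**Working it through.** The plan states no cost, effect size or variance, so it has no figure to reproduce. The check has three parts: timing, allocation and absenteeism.

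**Timing.** Six months is about 183 days, so the window runs from about day -183 to day 0. Day -15 lies inside it. The day 0 visit is on the boundary and is not one of the six control visits either.

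**Allocation of expenditure.** Let B be true six-month expenditure, unchanged by treatment, and W the cost of the work-up, additional to usual care. The ratio W/B is an assumption, taken from 0.02 to 0.30.

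- (a) Work-up in baseline expenditure, later programme items in treatment cost. Baseline is B + W and follow-up per half-year is B. Apparent saving = W/(B+W).
- (b) Work-up booked to treatment cost, and later programme items likewise. Baseline and follow-up are both B. Apparent change = 0.
- (c) Programme items counted as expenditure in both periods. Six control visits over 24 months are 6/4 = 1.5 per half-year. If each costs as much as the work-up, follow-up per half-year is B + 1.5W. Apparent change in expenditure = 0.5W/(B+W), an increase.

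| W/B (assumed) | (a) apparent saving | (b) | (c) apparent increase |
|---|---|---|---|
| 0.02 | 0.02/1.02 = 2.0% | 0 | 0.01/1.02 = 1.0% |
| 0.05 | 0.05/1.05 = 4.8% | 0 | 0.025/1.05 = 2.4% |
| 0.10 | 0.10/1.10 = 9.1% | 0 | 0.05/1.10 = 4.5% |
| 0.20 | 0.20/1.20 = 16.7% | 0 | 0.10/1.20 = 8.3% |
| 0.30 | 0.30/1.30 = 23.1% | 0 | 0.15/1.30 = 11.5% |

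These figures are per half-year. If the baseline were multiplied by 24/6 = 4 to match the follow-up, the single work-up would enter as 4W and the percentages would not change. The plan states no such scaling.

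**Absenteeism.** Here there is no separate programme component, so visit-related hours count in both periods. The baseline half-year holds one programme visit (day -15). Follow-up holds 1.5 doctor control visits per half-year. Dietitian visits follow from the stage lengths in section 6 and the frequencies in section 7.2:

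- BMI 30 to 35: 2 months fortnightly (4) + 4 months monthly (4) + 18 months semi-annual to quarterly (3 to 6) = 11 to 14. With the doctor visits, (6+11)/4 = 4.25 to (6+14)/4 = 5.0 per half-year.
- BMI above 35: 6 + 6 + 15 months of maintenance (2.5 to 5) = 14.5 to 17. With the doctor visits, (6+14.5)/4 = 5.1 to (6+17)/4 = 5.75 per half-year.

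Programme visits are therefore more frequent after day 0 than before it, and hours lost to them push towards more absence during follow-up. The fortnightly doctor visits that section 6 describes for stage 1 would widen the gap.

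**The case against.** The strongest reply is that the plan already has a place for the work-up. The treatment-cost list includes a count of laboratory tests with no start date, and a panel ordered to screen for the diet fits there naturally. The programme physician may be neither a general practitioner nor a specialist in the sense of the expenditure list, and an ECG is in no cost list at all. A careful analyst could adopt allocation (b) without changing a word. This stands as far as it goes: inflation of the baseline is a risk, not a fact. It does not settle the matter, because laboratory tests are in both lists with no rule between them, and the visit itself is assigned to neither.

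Two stronger readings are tempting. A reader might infer that the error always produces a saving, but allocation (c) reverses the sign. A reader might also infer a false fall in absenteeism, but the visit schedule points the other way. Ending only the baseline window early would make this worse for absenteeism, since programme-visit hours would leave the baseline and stay in follow-up.

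It is also fair to say that comparing a 6-month period with a 24-month one without a stated common time unit is a separate and larger problem, and that one visit and one panel at a known date can be reallocated without new data.

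**Conclusion.** The concern holds as an unassigned cost that can bias the primary expenditure comparison, not as a demonstrated bias. The day -15 visit and panel lie in the pre-treatment window, the plan does not exclude them, and one plausible way of applying section 10.2 books them as usual-care expenditure. Under that allocation the apparent saving with no true change is 2.0% to 23.1%, for assumed work-up costs of 2% to 30% of six-month expenditure, and programme cost is understated by the work-up. The range assumes that the work-up is additional to usual care and that later programme items go to treatment cost. The laboratory panel is the firmest ground, the physician visit is less certain, and the ECG counts only if it is costed at all.

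A reader might quote the effect on laboratory counts instead: with an assumed one usual panel per six months, one extra panel gives a false fall of 1/(1+1) = 50%. That is not the primary quantity, which adds laboratory tests to drugs, complications, admissions and visits.

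This deserves correction before analysis, because afterwards the allocation could be chosen with the results in view. It ranks below the faults that must be fixed.

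**What to change.** In section 10.2, state four rules:

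1. The pre-treatment expenditure window is the 6 months ending the day before the pre-inclusion visit (day -16 on the planned schedule), anchored on each patient's actual visit date.
2. The day -15 and day 0 visits and tests are part of the cost of the weight loss treatment. Say whether the ECG is costed.
3. Programme visits and tests are excluded from healthcare expenditure in both periods and appear only in treatment cost.
4. Hours of absence due to programme visits are excluded in both periods, or reported separately in both.

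The cost is a few sentences and a date cut. Records must reach back about 183 + 15 = 198 days instead of 183. Absence hours must be split by cause; section 7.2 already has dietitians record cause, but it names days, so the form should capture hours for programme visits. Compared with booking the work-up as baseline expenditure, the reported saving and programme cost become slightly less favourable to the method. Patient care is unaffected.

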7.3. Duration of study

For each patient initiating treatment, a minimum follow-up period of 2 years will be observed.

8. SOURCE OF INFORMATION AND DATA MANAGEMENT.

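### Section 10.2 names independent-group tests for before-after comparisons within one cohort, and states no analysis set or missing-data rule to fix which patients are compared

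*Combined protocol and SAP*

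**What the plan says.** Section 4 describes a single observational cohort followed for two years, with no randomization, and no comparator appears in the plan. Section 5.3 expects 200 patients.

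Section 10.2 sets out the comparisons. For the primary objective, healthcare expenses and absenteeism from the six months before treatment "will be compared with data recorded at follow-up visits over the 2-year follow-up". Drug doses and numbers of drugs are compared in the same before-after way. The secondary analysis proceeds by "comparing the anthropometric parameters of the initial visit with those of the follow-up visits", and SF-12 changes run from the initial visit to the end of each stage.

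One list of tests then serves all objectives: Chi square or Fisher for qualitative variables, and Student's t-test (worded for two groups) or one-way ANOVA for quantitative ones. If their conditions fail, "the non-parametric Mann-Whitney U test (2 groups) or the Kruskal-Wallis test (for 3 or more groups) will be used".

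The statistical section names no analysis set, no method for missed visits and no rule for incomplete cost records. On dropout, section 7.2 says: "In case of early withdrawal from the study, the doctor will write the dropout date and the reason, in study completion form".

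**The concern.** The two sides of each comparison are the same people measured at different times. A test for independent groups ignores the correlation between a patient's own values, so its standard error and p-value are wrong for this design.

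There is a second consequence. An unpaired test accepts every value available at each time. Nothing in section 10 limits the baseline side to patients who also have the later value. Once patients leave, the contrast can mix real change with a difference between those who stay and those who enrolled. There is no comparator to show whether that has happened.

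For the primary cost and absenteeism outcomes the matching problem is time. The plan does not say how a six-month window is scaled against a two-year one, or what happens to months that were not observed.

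**Working it through.** **Inputs from the documents.** 200 patients (5.3); one cohort (4); two years of follow-up per patient (7.2, 7.3); a six-month pre-treatment window and significance level 0.05 (10.2; two-sided assumed). No effect size, SD, power, correlation or dropout rate is given, so the 200 cannot be reproduced. Dropout d, correlation ρ and selection strength below are assumptions.

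**1. Precision with complete data and equal SDs.** Unpaired SE = SD·√(2/n). Paired SE = SD·√(2(1−ρ)/n). Their ratio is 1/√(1−ρ). The actual size of a nominal 0.05 unpaired test is 2[1−Φ(1.96/√(1−ρ))]. For a true change of 0.2 SD and n = 200, paired power is Φ(0.2·√(200/(2(1−ρ)))−1.96) and unpaired power is Φ((0.2·√(200/2)−1.96)/√(1−ρ)).

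| ρ | SE ratio | Actual size | Power, unpaired | Power, paired |
|---|---|---|---|---|
| 0.3 | 1.20 | 0.019 | 52% | 67% |
| 0.5 | 1.41 | 0.0056 | 52% | 81% |
| 0.7 | 1.83 | 0.0003 | 53% | 96% |

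The error is on the conservative side: power is lost and false positives are not created.

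**2. Who is on each side once patients leave.** Let B be a baseline mean and F a follow-up mean. Since B(all) = (1−d)·B(stay) + d·B(leave):

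F(stay) − B(all) = [F(stay) − B(stay)] + d·[B(stay) − B(leave)].

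If stayers and leavers differ by an assumed 5 kg at baseline, the added term is 0.2 × 5 = 1.0 kg at d = 20% and 0.5 × 5 = 2.5 kg at d = 50%, in either direction. It is zero if they do not differ.

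A simulation (4000 runs per setting, 200 patients, no true change, ρ = 0.8) varied the odds ratio (OR) of dropout per baseline SD:

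| Dropout | OR | All enrolled vs attenders: shift (SD), rejected | Paired completers: shift (SD), rejected |
|---|---|---|---|
| 20% | 1.0 | 0.00, 0% | 0.00, 5% |
| 20% | 2.0 | −0.10, 4% | +0.03, 8% |
| 30% | 2.0 | −0.15, 17% | +0.04, 10% |
| 50% | 1.0 | 0.00, 0.4% | 0.00, 5% |
| 50% | 2.0 | −0.25, 55% | +0.06, 17% |

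At 30% dropout and OR 2.0 the identity splits −0.152 into the stayers' own change of +0.038 (regression to the mean) and a baseline-selection term of −0.152 − 0.038 = −0.190. Pairing removes the second part only.

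**3. Dropout related to outcome.** If leavers have r times the stayers' benefit, the stayers' mean change divided by the all-patient mean change is 1/((1−d)+d·r). For d = 20% and 50% this is 1.25 and 2.00 at r = 0, 1.11 and 1.33 at r = 0.5, 1.00 at r = 1, and 0.95 and 0.89 at r = 1.25. Paired completers give the same ratios, so the choice of test is not the cause.

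**4. Observed time for cost and absenteeism.** Before treatment: 200 × 0.5 = 100 patient-years. Planned follow-up: 200 × 2 = 400. With dropout spread evenly over 24 months, each leaver loses one year on average. Then 40 to 100 leavers (20–50%) lose 40 to 100 patient-years, or 10–25%. At a constant true rate, counting that time as zero would lower the apparent annual rate by 10–25% with no real change.

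**The case against.** Student's t-test can be run paired, and the plan does not forbid it. That is fair, but the wording for two groups and the Mann-Whitney and Kruskal-Wallis fallbacks point to independent samples. A paired plan would normally fall back on Wilcoxon signed-rank or Friedman.

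Four stronger readings are tempting, and the documents do not support them.

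- A reader might infer that the plan sets month-24 attenders against everyone enrolled. No sentence says so. It is only what unpaired tests do by default. For SF-12, and for clinical parameters in section 9.2, the plan speaks of changes, which suggests within-patient differences.
- A reader might infer that the named tests inflate the benefit by 1.25 to 2.00 times. Step 3 shows that ratio would be the same with paired completers, and it needs leavers to keep no benefit, which the documents do not show.
- A reader might infer that ignoring pairing produces false positives. With complete data and positive correlation it does the opposite. With dropout the comparison is less simple: at d = 50% the unpaired SE relative to that of paired completers is √(0.75/(1−ρ)), which falls below 1 when ρ is under 0.25. Such a low correlation is possible for costs or absence days.
- A reader might infer that data collection ends when a patient stops the programme. Section 7.2 does say that the staff recording data "will regularly see the patient in the face-to-face visits at the Pronokal centre", and its sentence on dropout concerns withdrawal from the study. But section 8.1 also names medical records as a source. The available text is silent on patients who stop the programme but still consent.

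Part of section 8 and the annexes were not available to this review and could hold a data-handling rule.

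**Conclusion.** The point holds on the choice of tests. For before-after comparisons in one cohort, section 10.2 names independent-group methods, and nothing in the statistical section fixes which patients form each side. With complete data the cost is power: at an assumed correlation of 0.5 and a true change of 0.2 SD, 52% against 81%. With dropout related to baseline, the default available-case contrast can show a change that did not occur, by d times the baseline difference. With dropout unrelated to baseline, that term vanishes. Neither the direction nor the size can be computed from the documents. The change should be made before analysis. Confidence is medium, because the t-test could be run paired and every size rests on assumed inputs.

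**What to change.** In section 10.2:

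1. Replace the independent-group tests with a repeated-measures mixed model on all available visits, for all patients who start the programme. For simple two-time comparisons use the paired t-test, Wilcoxon signed-rank or McNemar test, and label them completer analyses.
2. Express healthcare cost and absenteeism per unit of observed time in both the six-month pre-treatment window and follow-up. Do not count unobserved time as zero.
3. Report the number observed at each visit. Add one conservative sensitivity analysis for dropouts that covers cost and absenteeism as well as weight, for example with unobserved values set to the patient's own pre-treatment level.

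Optional, outside the core fix: section 7.3 commits that "For each patient initiating treatment, a minimum follow-up period of 2 years will be observed". Section 7.2 could state whether collection from medical records continues for consenting patients who stop the programme.

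The cost is a few paragraphs of text and slightly more analysis work. The mixed model still assumes that dropout depends on observed data, which is why the sensitivity analysis is needed. The resulting estimate may be less favourable.
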